MRQ 1a. Among patient participant, CHW and primary care provider (PCP) stakeholders, what are the barriers and facilitators to use of the intervention and how do these compare according to performance level, namely, patient quitters, PCP prescribers, and CHW facilitators?

MRQ 1b. Among patient participant, PCP, and CHW stakeholders, what are the barriers and facilitators to use of the intervention and how do these compare according to level of engagement?

MRQ 2a. How do the PCPs, grouped by primary care clinic, differ by performance level and how do their experiences with the intervention, and the barriers and facilitators compare across these groups?

MRQ 2b. What is the association between engagement with the AD intervention among high or low performers, and how did barriers and facilitators experience compare across these groups?

QQ (Qualitative Question) 3. What barriers and facilitators do stakeholders, such as clinical, payor and policy leaders anticipate impacting the implementation of the integrated smoking cessation treatment?

III. SUBJECT SELECTION

The intervention will be implemented at the primary care clinic level. Providers at primary care clinics that provide care to smokers with SMI who receive psychiatric rehabilitation through the CBFS and ACT programs administered through Bay Cove Human Services in Boston and Vinfen Corporation in Cambridge will be identified by the agencies, Bay Cove and Vinfen and

randomly assigned to receive either AD for smoking cessation treatment to those with SMI or no intervention (TAU). We estimate that approximately 26-30 clinics will be assigned to AD and 13-15 to TAU. Patients who receive primary care through clinics assigned to the AD intervention will be randomized to be offered support from a CHW (AD+CHW) or not (AD).

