As noted above, after enrollment was complete, but before the randomization, the protocol was amended because 13% (155 of 1165) of enrolled participants received primary care at 111 clinics that each served ≤ 2 enrolled participants. Because it was beyond the scope of the project to provide AD to so many clinics, prior to randomization, the decision was made and approved by the sponsor to include these 155 enrolled participants in a second cohort in a stratified randomization, such that Cohort 1 (AD-eligible) comprised participants seen in primary care clinics serving ≥ 3 enrolled participants described above. Cohort 2 (AD-ineligible) comprised participants whose primary care clinic served ≤ 2 enrolled participants who were randomized to CHW or TAU in a 1:1 ratio.

The patient population will consist of approximately 1300 adult outpatient smokers with SMI who receive psychiatric rehabilitation services through CBFS and ACT programs at Bay Cove Human Services and Vinfen Corporation. This includes adults primarily with schizophrenia spectrum disorders and bipolar disorder.

Inclusion/exclusion criteria:

Primary care clinics/physicians/nurses/care team: There are no requirements for clinics to be included or excluded except that they provide medical care to people with SMI who smoke and who are served by the CBFS and ACT psychiatric rehabilitation systems of Bay Cove and Vinfen. There are no exclusion criteria for prescribers related to specialty (e.g. internal medicine, psychiatry, pulmonary medicine, family medicine, clinical nurse specialist), experience with smoking cessation therapies, or experience working with people with SMI.

Since the patient and their prescriber will decide together on the timing of initiation of any pharmacotherapeutic cessation aid, there will be no exclusion criteria for patients due to medical illness or psychiatric symptom severity or stability or substance use.

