Sample size estimate based on hypothesized effect size: We estimated the statistical power of the trial using computer simulation methods. This approach has an advantage over analytic power estimates in that it easily incorporates varying cluster sizes and can employ the exact analysis method contemplated in the planned study. In brief, we simulated the trial 1000 times, including the anticipated effect of the intervention and the eventual data analysis. We repeated this process many times, and the proportion of times we rejected the null hypothesis of no trial effect is our estimated power. We used a conservative approach as follows. We began with a conservative estimate of 40 clinics (we may to enroll up to 60 clinics) in the study and 1100-1170 enrolled patients who are expected to agree to provide baseline data from a pool of approximately 1300 smokers with SMI in the participating rehabilitation programs. Our analysis plan will use information from those who leave the system without data from early termination visits using multiple imputation, but for the purpose of sample size calculation, we assumed no such information, so we use a sample size of 900 patients, which allows for 10-12% to refuse to participate at enrollment and 10-12% attrition per year. While 5% of those served by CBFS have left the system per year over the prior 3 years because they move out of the geographic area, die, do not engage with the rehabilitation team, or are otherwise lost to follow up, we assumed, for the purposes of power calculations, that 10-12% of the patients would leave the study each year. Thus these estimates are conservative.

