We then assumed that the proportion of patients who quit smoking in each clinic followed a logistic regression model with a clinic effect that was normally distributed and was different in the intervention groups. The parameters of this model were chosen to give a conservative abstinence rate at the Year Two and Three assessments in the AD+CHW group of 15% and overestimate the expected abstinence rate in the TAU group at 5%. The estimated quit rate in the AD+CHW group of 15% is lower than that observed in clinical trials. It assumes that 65% of the smokers who receive AD+CHW will make a quit attempt and that 30% of those who make an attempt will achieve abstinence [28, 37]. This estimated cessation attempt rate is conservative, as 80% of those queried at MGH Schizophrenia Education Day reported they would make a cessation attempt if aided by their doctor or prescribing nurse. The estimated abstinence rate among those who try to quit is also conservative, as we observed 42% abstinence rates in our recent open label varenicline trial and over 50% abstinence rates in our trial of bupropion plus NRT patch and gum in a similar DMH served SMI population [26, 37]. Further,

we assume that over six months roughly 20% of those who attain abstinence will relapse despite availability of ongoing treatment. [36]

These assumptions are conservative, as 80% of smokers with SMI report that they want to try to quit smoking and would make an attempt if aided by their prescriber, while we assumed 65% would actually try, and we found a 42% cessation rate with 12 weeks varenicline treatment and over 50% abstinence rate with bupropion plus NRT, but assume a 30% cessation rate.

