The quit rate of 5% in the usual care group is also conservative, since the average cessation rate across 6 randomized clinical trials summarized in the Tsoi et al Cochrane Review of smoking cessation studies in adults with schizophrenia was 4% at 12 weeks among smokers with SMI who expressed intention to quit smoking within 30 days, set a quit date and received placebo and behavioral smoking cessation treatment. Those in the usual care group are unlikely to receive similarly intensive behavioral smoking cessation treatment [28], further supporting the conservative nature of the estimated 5% quit rate in the usual care group. We used this higher than expected cessation rate for the TAU group in the simulation in order to consider the possibility that publication of the results from our previous work [28, 37, 40] may change clinical practice without the concerted effort proposed under this project, though this has not been observed to date.[3] The variation of the parameter that determined the “clinic effect” was chosen so that the standard deviation of the probability of quitting among different clinics was 9% in the AD+CHW group and 3% in the usual care group. This differential variability reflects the floor effect of the small proportion of quitters in the usual care group, and the variability associated with the intervention in the AD+CHW group. The resulting overall intraclass correlation coefficient of 3% is typical for this type of study [115]. We then used this logistic model to simulate whether each patient would be abstinent at the Year Two assessment.

Our simulation resulted in over 95% power to detect a significant difference in the proportion of patients abstinent at the Year 3 assessment. As a sensitivity analyses, we increased the standard deviation of the parameters governing the variation in the quit rates by a factor of 50%. This would increase the overall intraclass correlation to 7% and reduce the power to 87%. If we considered only patients with schizophrenia spectrum disorders, which is a planned subgroup analysis, we would have 77% of the patients in this subgroup analysis. This would still give 94% power to detect an effect in those with a schizophrenia spectrum disorder.

Missing data

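### The powers in VII.4 (over 95%, 87%, 94%) are too favourable for the current primary comparison in Cohort 1, and the overall ICC behind them is not defined

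*Combined protocol and SAP*

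**What the plan says.** VII.4 describes a simulation, chosen because "it easily incorporates varying cluster sizes and can employ the exact analysis method contemplated in the planned study". Its inputs are:

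- **Clinics:** "We began with a conservative estimate of 40 clinics (we may to enroll up to 60 clinics) in the study".
- **Patients:** "so we use a sample size of 900 patients, which allows for 10-12% to refuse to participate at enrollment and 10-12% attrition per year".
- **Rates:** the parameters were "chosen to give a conservative abstinence rate at the Year Two and Three assessments in the AD+CHW group of 15" per cent, with TAU at 5%.
- **Clinic variation:** SD of the quit probability 9% in AD+CHW and 3% in TAU, said to give an overall ICC of 3%.

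The headline result is "Our simulation resulted in over 95% power to detect a significant difference in the proportion of patients abstinent at the Year 3 assessment". Raising the SDs by half is said to lift the ICC to 7% and lower power to 87%. The schizophrenia-spectrum subgroup, 77% of patients, is given 94%. VII.4 does not state the split of the 900 patients between arms, the efficacy alpha, the test, or how the overall ICC is formed.

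The design is set out elsewhere. III Subject Selection says: "We estimate that approximately 26-30 clinics will be assigned to AD and 13-15 to TAU". VII.1 assigns one third of eligible clinics to TAU and two thirds to AD, and offers CHW support to half of the participants in AD clinics. III also records that "13% (155 of 1165) of enrolled participants received primary care at 111 clinics that each served ≤ 2 enrolled participants", and that "Cohort 1 (AD-eligible) comprised participants seen in primary care clinics serving ≥ 3 enrolled participants described above". Under VII.1 the remaining participants (Cohort 2) enter only a secondary factorial analysis.

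VII.3 gives separate three-arm powers in Tables 1–2, with AD+CHW at 16% or 18%, TAU at 5% or 3%, and ICC .03.

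**The concern.** The primary comparison sets about one third of Cohort 1 against another third. VII.4 starts from 900 patients, never says how many are in each of the two compared arms, and does not mention the loss of Cohort 2. If its powers belong to a larger comparison, the type II error is understated for the plan's own conservative case. A reader weighing a null result, especially with large clinic variation or in the subgroup, would rely on these figures. The unstated alpha and ICC weighting also prevent anyone from reproducing them.

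**Working it through.** **Assumptions not in the documents.** Two-sided 0.05 (the only threshold given is the DSMB's 2-tailed 0.05 for safety, in IX). Clinic sizes are either equal or have coefficient of variation (CV) 0.6–0.7. As in VII.4, nothing is gained from multiple imputation. Results are in the order base / larger variation / subgroup.

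**Formula.** With n patients in an arm and m per clinic in that arm, effective size is n/[1 + (m − 1)ρ]. Power = Φ(0.10/SE − 1.96), where SE² = 0.05×0.95/n₁ + 0.15×0.85/n₂ on effective sizes. For unequal clinics, m becomes m(1 + CV²).

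**1. Reproducing the stated figures.** Try 900 patients as 450 and 450, in 20 + 20 equal clinics of 22.5.
- ρ = .03: 450/1.645 = 273.6 per arm, 97.7%.
- ρ = .07: 450/2.505 = 179.6, 89.3%.
- Subgroup (346.5 per arm, ρ = .03): 232.6, 95.4%.

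With a pooled null variance the results are 97.5 / 88.8 / 95.1%. A logistic mixed-model simulation with the stated SDs and a Wald test gives 96.6 / 86.8 / 93.7%. This layout is therefore close to all three stated figures.

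**2. Size of the current comparison.** 1165 − 155 = 1010 enrolled. 1010 × 0.90² = 818 and 1010 × 0.88² = 782. One third of these is about 261–273 per arm. Clinics: 26 + 13 = 39 to 30 + 15 = 45.

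**3. Common ICC, Cohort 1.** Take 782 patients in 40 equal clinics: 19.55 per TAU clinic, and 9.775 AD+CHW patients per AD clinic.
- ρ = .03: TAU 260.7/1.5565 = 167.5; AD+CHW 260.7/1.263 = 206.3; SE = .0300; 91.5%.
- ρ = .07: 260.7/2.2985 = 113.4 and 260.7/1.614 = 161.5; SE = .0348; 82.0%.
- Subgroup (200.7 per arm): 141.2 and 167.8; 85.6%.

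With 818 patients in 45 equal clinics the results are 93.1 / 84.9 / 87.6%. With CV 0.6, 782 patients and 40 clinics they are 88.8 / 75.6 / 82.7%. The band is about 89–93 / 76–85 / 83–88%.

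Method matters here. With a pooled null variance and about 780 patients in 40–45 equal clinics, the formula gives 89–90 / 77–79 / 83–84%. One set of mixed-model simulations gives 90–93 / 81–88 / 81–88%. Another, at ICC 7% with 800 patients in 42 clinics, gives 83% with equal clinics and 82% at CV 0.7.

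**4. Stated clinic SDs, Cohort 1.** These are mixed-model simulations with logit-normal clinic effects calibrated to 5%/3% and 15%/9%. Logit SDs are multiplied by 1.5 for the sensitivity case. There were 2000 runs per cell.

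| 40–45 clinics, N = 782–818 | Base | SDs × 1.5 | Subgroup |
|---|---|---|---|
| Stated in VII.4 | >95 | 87 | 94 |
| Equal clinics | 87.6–90.9 | 73.7–79.1 | 82.1–85.4 |
| CV 0.7 | 83.8–88.4 | 68.9–76.6 | 76.6–79.7 |

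**5. ICC implied by the SDs.**
- TAU: 0.03²/(0.05×0.95) = 1.9%. AD+CHW: 0.09²/(0.15×0.85) = 6.4%. Simple mean 4.1%; pooled 0.0045/0.0875 = 5.1%.
- Sensitivity case: 4.6% and 13.2%. Simple mean 8.9%; pooled 10.9%.
- Weighted 2:1 toward TAU: (2×1.9 + 6.4)/3 = 3.4% and (2×4.62 + 13.20)/3 = 7.5%, which are compatible with the printed 3% and 7%.

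**The case against.** **Three-arm power is already given.** True. Table 1's .96 for 16% against 5% is about .93–.96 in Cohort 1 with equal clinics, so the tables stand. They have no 15% case, no larger-variation case and no subgroup, so they do not support the three figures in VII.4.

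**More clinics or a one-sided test would close the gap.** Partly. With 60 equal clinics, the stated SDs give 91–94 / 81–85 / 85–87%. The formula at a common ICC gives 94 / 88–89 / 88–89%, which reaches the 87%. One-sided 0.05 with 40–45 equal clinics and the stated SDs gives 94–95 / 84–88 / 89–92%. But VII.4 bases its calculation on 40 clinics, III expects 39–45, and sidedness is not stated.

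**The sensitivity result depends on the reading.** This stands. A reader might infer that sensitivity power is below 80% outright. By the formula in step 3 that holds only with unequal clinics. Otherwise it needs the SD reading or the more cautious pooled variance. The mixed-model simulations at a common 7% stay above 80%, and the top of one range (88%) even touches the stated 87%.

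**The two-arm origin is unproven.** This also stands. A reader might infer that VII.4 is a leftover two-arm calculation, but no section says so. The match is good only with equal clinics and some tests. At CV 0.7 the two-arm simulation gives 94.3 / 83.2 / 91.3%, and at a common ICC of 7% it gives 92–95% rather than 87%. The shortfall in Cohort 1 does not depend on this inference.

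**Little turns on it.** Cohort 2 was formed after enrolment closed, VII.3 expects 16–18% against 3–5%, and VII.2 already calls the diagnosis hypotheses underpowered and exploratory. That limits the weight of the point but does not make the stated powers right.

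**Conclusion.** The concern holds for VII.4 only. At 15% against 5%, two-sided 0.05 and 40–45 clinics, the bands for Cohort 1 fall short of all three stated powers under both readings. The 87% is the figure most nearly met.

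Type II error, in the same order as the powers:

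- **Implied by VII.4:** under 5% / 13% / 6%.
- **Stated SDs:** about 9–16% / 21–31% / 15–23%.
- **Common ICC:** about 7–11% / 15–24% / 12–17%.

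The result rests on the assumed alpha, 10–12% yearly attrition, and clinic sizes that the documents do not give.

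Two further inferences are not supported. The trial is not shown to be underpowered, because base-case power exceeds 80% in every run. The ICCs of 3% and 7% are not shown to be wrong, because a 2:1 weighting toward TAU gives values that round to them. What is missing is the definition.

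**What to change.** Re-run the existing simulation for the primary comparison: Cohort 1, three-arm allocation, 15% against 5%, actual clinic numbers and sizes, and 10–12% yearly attrition. State alpha, sidedness and the test. Replace the three powers in VII.4 with the results; the ranges here are indicative only. Alternatively, keep the old figures, label them with the layout they belong to, and refer to Tables 1–2 for three arms. State how the overall ICC is weighted, and whether the sensitivity case is defined by the SDs or by the 7%.

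The cost is one re-run and a text edit. The stated powers become less favourable. Enrolment, test and estimand stay as they are.
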